Appendix 1: Sample log table – all matrices

- [REDACTED]
- Removal of urinalysis sampling at V4, 101, 103, 105, EOT and EOS.
- [REDACTED]
- [REDACTED]

Appendix 3: Clinically notable laboratory values

- Addition of this new appendix to define the criteria to be used as a guidance for notable abnormalities of key laboratory tests.
- [REDACTED]

Minor changes have been made throughout the protocol to improve clarity.

Changes to specific sections of the protocol are shown in the track changes version of the protocol using strike through red font for deletions and red underlined for insertions.

A copy of this amended protocol will be sent to the participating Institutional Review Boards (IRBs)/Independent Ethics Committees (IECs) and Health Authorities.

The changes described in this amended protocol require IRB/IEC approval prior to implementation.

The changes herein affect the Informed Consent. Sites are required to update and submit for approval a revised Informed Consent Form (ICF) that takes into account the changes described in this protocol amendment. Novartis will provide an updated model ICF to sites.

Amendment 1 (May 2015)

Amendment rationale

The purpose of this amendment is to correct minor inconsistencies identified during health authority and ethics committee reviews, and to provide some clarifications on study assessments.

At the time of implementing this amendment, 3 patients had begun treatment; none were affected by changes made to the protocol. The changes described in this amendment do not affect the objectives of the study, impact the safety of the subjects or change the analysis of the study data. Some adjustments have been made to inclusion and exclusion criteria as a result of experience so far with the population required for this study.

Changes to the protocol

Protocol Synopsis

- Amended to reflect changes throughout the protocol

Assessment Schedule

- Addition of visit windows.
- Addition of Informed Consent to assessment schedule (already present in protocol but previously omitted from assessment schedule).
- [REDACTED]
- [REDACTED]
- Amendments due to change in follow-up period for patients continuing to the extension:
 - Movement of height measurement and [REDACTED] from EoS visit to EoT visit to provide data for extension study baseline.
 - Removal of footnote for prematurely discontinuing patients to only return for EoS visit.
 - Addition of footnotes stating that EoT visit will occur 4 weeks after last dose and will be the last visit for patients continuing to the extension study, and EoS visit will occur 4 weeks after EoT visit except for patients continuing to the extension study.
- ‘Study Completion information’ changed to ‘Phase Completion’ and assessment added at Baseline V2 and EoT to be in compliance with current database requirements.

Section 3.1 Study design

- Correction to add follow-up period to the diagram.
- Correction to assessments at Day 1 due to inconsistency with the Assessment Schedule.
- Addition of information on observation period following dosing on ‘Other Dosing Visits – Days 29, 57, 85, 113 and 141’.

- Explanation that patients continuing to the extension study will move directly from EoT visit to Visit 1 of the extension.
- Clarification that EoS visit will occur only for those patients discontinuing from the study prematurely or those not continuing to the extension study.
- Addition of information on planned extension study.

Section 3.6.1 BYM-related risks

- Text describing a standardized dermatology assessment removed. This is no longer needed as adverse event recording is sufficient.

Section 4.1 Inclusion criteria:

- Inclusion criterion #6: Dietary criteria to apply only at baseline, allowing correction of nutritional deficiency during screening period if appropriate.

Section 4.2 Exclusion criteria:

- Exclusion criterion #5: Amendment to state that intraocular surgery or intraocular laser procedures for refractive corrections are excluded.
- Exclusion criterion #6: Vitamin D criteria to apply only at baseline, allowing correction of low vitamin D levels at screening if appropriate.
- Exclusion criterion #11: Addition of inclusion body myositis in the examples for exclusion.
- Exclusion criterion #12: Addition of other systemic autoimmune disease requiring immunosuppressive therapy or corticosteroids to exclusion.
- Exclusion criterion #35: Amendment to allow patients receiving testosterone replacement therapy.
- Exclusion criterion #39: Clarification that medication exclusion applies prior to screening.
- Exclusion criterion #40: Clarification to exclude patients taking a systemic VEGF inhibitor and the acceptability of intravitreal use.

Section 5.5.1 Patient numbering

- Correction and clarification of randomization process with IRT system.

Section 5.5.3 Handling of study treatment

- Adjustment of concomitant vitamin D requirements to allow for sourcing in all countries.

Section 5.5.10 Discontinuation of study treatment

- Amendment of study completion requirements for patients who discontinue treatment early to ensure compliance with required safety follow-up timelines and consistency with the planned extension study.

Section 6.2.2 Nutritional supplement

- Adjustment of concomitant vitamin D requirements to allow for sourcing in all countries.
- Addition of low vitamin D correction with a loading dose.

Section 6.5.3 6 minute walk test

- Text added to clarify the conditions under which a test could be repeated.

Section 6.5.6 Patient Reported Outcomes

- Clarifications of PRO terminology

- [REDACTED]

Section 6.6.2 Vital signs

- Clarification that vital signs should be measured on the same arm at each visit where possible.

Section 6.6.4 Laboratory evaluations

- Clarification of situations where repeat assessments can be performed.
- Addition of creatinine to the chemistry panel to support the evaluation of eGFR for inclusion/exclusion.

Section 6.6.7 Pregnancy

- Removal of requirement for sexually active men to use a condom during the course of the study in alignment with the rest of the bimagrumab program, as there is no associated risk with this antibody.

Section 8.5 Adjudication committee

- Addition of orthopedic event adjudication

Section 10.2 Informed consent procedures

- [REDACTED]

Appendix 1: Sample log table

- Corrections to blood volumes following final setup and reconciliation with the central lab, and correcting an error which occurred during insertion of the table. [REDACTED]

- [REDACTED]

[figure not shown]
[figure not shown]

Protocol synopsis

Protocol number	CBYM338E2202
Title	A 28 week, randomized, double-blind, placebo-controlled, two-part, multi-center, parallel group dose range finding study to assess the effect of monthly doses of bimagrumab 70, 210, and 700 mg on skeletal muscle strength and function in older adults with sarcopenia (InvestiGAIT).
Brief title	Dose range finding study to assess multiple doses and evaluate safety and tolerability of bimagrumab in patients with sarcopenia.
Sponsor and Clinical Phase	Novartis Phase II
Investigation type	Drug
Study type	Interventional
Purpose and rationale	
The purpose of this study is to determine the efficacy of repeat dosing with multiple dose levels of bimagrumab on patient function, skeletal muscle mass and strength in older adults with sarcopenia. In addition, this study will generate data on the safety, tolerability, [REDACTED] of bimagrumab in older adults with sarcopenia.
 
The randomized, parallel group, placebo-controlled design will allow an unbiased comparison between 3 different dose regimens of bimagrumab and placebo on changes in muscle quantity and patient physical function in a population of older adults with sarcopenia

Primary Objective(s)	
 To assess the effect of 24-weeks of bimagrumab treatment on patient physical function assessed by a change in the Short Physical Performance Battery (SPPB) total score from baseline to week 25 relative to placebo in older adults with sarcopenia.
Secondary Objectives	
 To assess the effect of multiple doses of bimagrumab on the safety and tolerability of bimagrumab administered over 24 weeks as measured by vital signs, clinical laboratory values, electrocardiogram (ECG), echocardiogram (in a limited number of patients), and adverse events (AE) compared to placebo in older adults with sarcopenia. To assess the effect of bimagrumab compared to placebo on improvement in physical performance as measured by change from baseline to week 25 in the 6-Minute Walk Test (6MWT) distance in older adults with sarcopenia. To assess the effect of bimagrumab compared to placebo on improvement in mobility as measured by change from baseline to week 25 in usual gait speed (GS) over 4 meters in older adults with sarcopenia. To assess the effect of bimagrumab on total lean body mass and appendicular skeletal muscle index (ASMI) measured by DXA, assessed by the change from baseline to week 25 compared to placebo in older adults with sarcopenia.

Study design	
A two-part, randomized, double-blind, placebo-controlled, parallel group study design with approximately 339 older adults with sarcopenia assigned to one of four treatment groups: placebo, bimagrumab 70 mg, bimagrumab 210 mg, or bimagrumab 700 mg.
 
The study will consist of a 20-day screening period followed by a 28-day run-in period, and a 24-week treatment period followed by a 4-week follow-up period. During the run-in period, all subjects will be introduced to a 3 times per week exercise program, daily vitamin D and oral nutritional supplementation, and the performance-based endpoints. Towards the end of the run-in period, subjects will be re-assessed for eligibility (utilizing the baseline eligibility criteria) and qualified subjects will enter the treatment phase to receive six monthly doses of assigned study drug.

Population	
The study population will be community-dwelling men and women ages 70 years and older meeting the criteria for sarcopenia as defined by the European Working Group on Sarcopenia in Older People (EWGSOP) (Cruz-Jentoft et al 2010) and Asian Working Group for Sarcopenia (Chen et al 2014).

Inclusion criteria	
 1. Written informed consent must be obtained before any assessment is performed; 2. Men and postmenopausal women aged 70 years or older at screening with self-reported mobility limitations such as difficulty standing up from a chair, walking for longer than 10 minutes on a flat surface or climbing a flight of stairs; 
 • Women are considered post-menopausal and not of child bearing potential if they have had 12 months of natural (spontaneous) amenorrhea with an appropriate clinical profile (e.g. age appropriate, history of vasomotor symptoms) or have had surgical bilateral oophorectomy (with or without hysterectomy) or tubal ligation at least six weeks ago. In the case of oophorectomy alone, only when the reproductive status of the woman has been confirmed by follow up hormone level assessment is she considered not of child bearing potential. 3. Gait speed over 4 meters of <0.8 m/s but ≥ 0.3 m/s at screening and baseline; 4. Appendicular skeletal muscle index (skeletal muscle in kg/ height in m^2) by DXA based on central reading: 
 • ≤ 7.26 kg/m^2 for men and ≤ 5.5 kg/m^2 for women to be assessed during screening. • ASIAN COUNTRIES ONLY: ≤ 7.0 kg/m^2 for men and ≤ 5.4 kg/m^2 for women to be assessed during screening; 5. Total SPPB score of ≤ 9 at screening and baseline; 6. Weigh at least 35.0 kg to participate in the study and have a body mass index (BMI) within the range of 15.0 – 32.0 kg/m^2; 7. Usual dietary intake ≥ 20 kcal/kg body weight and ≥ 0.8 g protein/kg per day over the 4 weeks prior to baseline estimated by an established method of diet assessment (i.e. 24 hour recalls, food records or similar)

Exclusion criteria	
Medical conditions limiting performance of physical assessments
 
1. History of a lower limb fracture (e.g. femur, tibia) within the past 6 months with persistent negative impact on lower extremity function or any significant impairment or disease adversely impacting gait (e.g. intermittent claudication in advanced peripheral vascular disease, spinal stenosis, or severe osteoarthritis of the knee or hip with joint pain not controlled with medication/injections that adversely impacts mobility);2. Confirmed diagnosis of significant psychiatric disease (e.g. dementia/Alzheimer's disease, schizophrenia, depression or bipolar disorder). Individuals with adequately treated depression are eligible for enrollment;3. A Patient Health Questionnaire – 9 (PHQ-9) score ≥ 10 at screening;4. Neurological injury/disorder with significant persistent functional deficit (e.g. stroke with hemiparesis, spinal cord injury, muscular dystrophy, polymyositis, dermatomyositis, myopathy/myositides, myasthenia gravis, Parkinson's disease, peripheral polyneuropathy);5. Intraocular surgery and laser procedures for refractive correction within 6 months prior to screening;6. Vitamin D deficiency defined as 25-OH-vitamin D levels < 12.0 ng/mL (30nmol/L) at baseline;7. Hemoglobin concentration below 11.0 g/dL (110g/L) for men or below 10.0 g/dL (100g/L) for women at screening. 
Medical conditions associated with muscle loss
 
8. Chronic kidney disease [estimated glomerular filtration rate (GFR) < 30 mL/min];9. History of confirmed chronic obstructive pulmonary disease with a severity grade > 2 on the Medical Research Council Dyspnea Scale;10. Confirmed rheumatoid arthritis or other systemic autoimmune disease requiring immunosuppressive therapy or corticosteroids > 10mg/d prednisone equivalent, acquired immunodeficiency syndrome (AIDS), or type 1 diabetes mellitus;11. History of or ongoing gastrointestinal diseases known to cause malabsorption of protein or energy, such as inflammatory bowel disease, celiac disease, short bowel syndrome, pancreatic insufficiency. Individuals in which the disease is well controlled with medication/enzyme supplements (e.g., pancreatic insufficiency) or dietary modification (e.g., celiac disease) are eligible for enrollment; 
Liver [REDACTED] related conditions
 
12. Abnormal liver function tests such as SGOT (AST), SGPT (ALT), alkaline phosphatase, or serum bilirubin (except Gilbert's Disease), [REDACTED]. The investigator should be guided by the following criteria:
• Any single transaminase may not exceed 3x the upper limit of normal (ULN). A single parameter elevated up to and including 3x ULN should be re-checked as soon as possible, and always prior to enrollment/randomization, to rule out any lab error.• If the total bilirubin concentration is increased above the ULN, total bilirubin should be differentiated into the direct and indirect reacting bilirubin. In any case, serum bilirubin should not exceed the value of 1.6 mg/dL (27μmol/L).• [REDACTED]
--------------------	--

	
[REDACTED]
 
13. Known history or presence of severe active acute or chronic liver disease (e.g., cirrhosis) or conditions with hepatotoxic potential (e.g. known gallbladder or bile duct disease, acute or chronic pancreatitis);
 
Cardiovascular conditions
 
14. Confirmed diagnosis of heart failure classified as New York Heart Association Class III and IV (e.g. dilated cardiomyopathy);
 
15. Myocardial infarction, coronary artery bypass graft surgery, percutaneous coronary intervention (e.g. angioplasty or stent placement), or deep vein thrombosis/pulmonary embolism within 12 weeks of screening. Patients with current/active unstable angina are excluded;
 
16. Severe cardiac valve disorders or defects (e.g. aortic or mitral stenosis);
 
17. Severe pulmonary hypertension uncontrolled with medication;
 
18. Clinically significant cardiac arrhythmia requiring medical intervention in the past 3 months (e.g. SVT, atrial fibrillation with RVR, AICD with discharge);
 
Other medical or living conditions
 
19. History of hypersensitivity to therapeutically administered antibodies.
 
20. Chest pain, severe shortness of breath, or occurrence of other safety concerns during the screening or baseline assessments.
 
21. Lack of peripheral venous access
 
22. Active cancer (i.e., under current treatment), or cancer requiring treatment in the last 5 years excluding nonmelanoma skin cancers or cancers with excellent prognosis (e.g., early stage prostate or breast cancer, carcinoma in situ of the uterine cervix);
 
23. Significant coagulopathy, platelet count less than 75,000/mm³;
 
24. Active systemic infection requiring hospitalization or treatment with i.v. anti-infectives or antibiotics within 4 weeks of screening;
 
25. Any chronic active infection (e.g., HIV, hepatitis B or C, tuberculosis, etc), to be confirmed prior to randomization. Subjects receiving chemoprophylaxis for latent tuberculosis infection are eligible for the study;
 
26. Active alcohol/drug abuse, or alcohol/drug treatment < 12 months prior to screening; subjects having successfully completed an alcohol/drug treatment program >12 months prior to screening with sustained abstinence are eligible;
 
27. Subject has any medical condition or laboratory finding during screening (e.g. an unexplained or clinically significant lab result), which, in the opinion of the investigator may interfere with participation in the study, might confound the results of the study, or pose an additional safety risk in administering bimagrumab;
 
28. Subject plans to move out of the study area within 12 months or be out of study area for > 4 weeks continuously;
 
29. Individuals who require routine and regular (e.g., daily) assistance from another person to complete one or more basic activities of daily living (basic ADL; bathing, dressing, toileting, feeding, grooming) regardless of where they reside. Assistance with instrumental ADL (i.e., shopping, meal preparation, housework) is permitted;

--	--

	
30. Subjects with a Mini Mental State Examination score < 21 at screening;
  
Prohibited medication
 
Investigational and reference therapy	Placebo, bimagrumab 70 mg, bimagrumab 210 mg, or bimagrumab 700 mg
Efficacy assessments	
• Short Physical Performance Battery (SPPB) to assess functional status• 6 minute walk test (6MWT) to assess functional status• 

	
 • Gait speed (GS) to assess functional status • Total lean body mass (LBM) and appendicular skeletal mass index (ASMI) assessed by DXA to measure lean body mass and skeletal muscle mass of the arms and legs, respectively. • Patient reported outcome questionnaires
Safety assessments	
 • Physical examination • Vital signs (heart rate, blood pressure) • Height and weight • Laboratory evaluations • Urinalysis • ECG • Echocardiography (at EOT only for patients enrolled prior to this amendment who have a baseline scan) • [REDACTED] • [REDACTED] • [REDACTED]
Other assessments	
 • [REDACTED] • [REDACTED]
Data analysis	
[REDACTED]
 
This is a two part study. Part-A will investigate the presence of a positive effect of maximum bimagrumab dose (700 mg) over placebo in change from baseline SPPB score at week 25. A positive effect of bimagrumab will be defined as a statistically significant effect over placebo and a clinically relevant improvement of ≥ 1 unit increase from baseline compared to week 25.
 
[REDACTED]

Key words	
Dose range finding study, effect, safety and tolerability, bimagrumab, sarcopenia, muscle, physical function

Assessment schedule

Study Phase	Screening	Run-In					Treatment												Follow-up								
		Baseline																	EoT	EoS							
Visit Numbers ¹	1	2*	3*	4	5*	101*	1015	102	103	104	105	106	107	108	109	110	111	112	113	114	115	116	117	118	119	120	
Month	-2			-1		1		2	3	4	5	6	7	8	9	10	11	12	13	14	15	16	17	18	19	20	
Week	-	-	-	-	-	1		3	5	9	13	17	21	25	29												
Day	-50 to -30	-29 to -23	-22 to -16	-15 to -10	-5 to -1	1	15	29	57	85	113	141	169*	197**													
Visit Window	-	-	-	-	-	+ 2 days	+ 2 days	+ 4 days	+ 4 days	+ 4 days	+ 4 days	+ 4 days	+ 4 days	+ 4 days	+ 4 days	+ 4 days	+ 4 days	+ 4 days	+ 4 days	+ 4 days	+ 4 days	+ 4 days	+ 4 days	+ 4 days	+ 4 days	+ 4 days	
Hours	-	-	-	-	-	pre-DOSE	0	pre-DOSE	0	pre-DOSE	0	pre-DOSE	0	pre-DOSE	0	pre-DOSE	0	pre-DOSE	0	pre-DOSE	0	pre-DOSE	0	pre-DOSE	0	pre-DOSE	0

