- The interim analysis may include additional endpoints of safety, efficacy, [REDACTED] and background treatments.

Section 3.2 Rationale for study design, Section 4.1 Inclusion criteria, Section 5.1.2 Additional study treatment, Section 5.5.3.2 Handling of other study treatments, Section 6.2 Dietary Requirement and throughout the protocol

- Protein supplementation terminology updated to oral nutritional supplementation.

[REDACTED]

Section 4.2 Exclusion criteria

- [REDACTED]
- Criterion #25 clarified to note that active infection results must be received prior to randomization.
- [REDACTED]

Section 5.5.6 Recommended treatment of adverse events

- [REDACTED].

Section 6.5.7 Mini Mental State Examination (MMSE)

- Clarified that MMSE is not required at baseline, as per the Assessment Schedule.

[REDACTED]

Section 9.4.2.1 Analysis for part-A

- Criterion 1 significant difference updated from one-sided 5% level to one-sided 2.5% level.
- The two-sided confidence interval of treatment vs placebo was updated from 90% to 95%.

Section 9.6 Sample size calculation

- Sample size calculations for Part A interim analysis updated.

Section 9.7 Power for analysis of key secondary variables

- Analysis of power for key secondary variables updated for gait speed and 6-minute walk test.

Section 15 Appendix 3: Clinically notable laboratory values

- 

Section 16 Appendix 4: Blinding and unblinding

- Footnote added to clarify that if the study is terminated following the interim analysis, blinding will follow the final database lock event guidelines.

Additional administrative clarifications and corrections have been made throughout the protocol for clarity.

Changes to specific sections of the protocol are shown in the track changes version of the protocol using strike through red font for deletions and red underlined for insertions.

IRBs/IECs

A copy of this amended protocol will be sent to the Institutional Review Board (IRBs)/Independent Ethics Committee (IECs) and Health Authorities.

The changes described in this amended protocol require IRB/IEC approval prior to implementation.

The changes herein affect the Informed Consent. Sites are required to update and submit for approval a revised Informed Consent that takes into account the changes described in this protocol amendment.

Amendment 2 (September 2016)

[figure not shown]
Amendment rational

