2.1 Primary objective

The primary objective is to assess the effect of 24-weeks of bimagrumab treatment on patient physical function assessed by a change in the Short Physical Performance Battery (SPPB) total score from baseline to week 25 relative to placebo in older adults with sarcopenia.

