3.1.2 Interim Analysis

An interim analysis will be performed on the bimagrumab 700mg and placebo groups at the completion of Part A to determine treatment efficacy. [REDACTED]

[figure not shown]
Primary analysis: To support the primary objective, the change in the Short Physical Performance Battery (SPPB) total score from baseline to week 25 will be compared between treatment groups.

Following criteria will be evaluated at the end of Part-A

- [REDACTED]
- [REDACTED]

Based on the planned use of Part A data for decision making, additional endpoints of safety (e.g., AEs, lab values, ECG), [REDACTED] background treatments (e.g., exercise, Vitamin D, diet), and efficacy (e.g., gait speed, 6MWT, [REDACTED], [REDACTED], LBM and ASMI by DXA, [REDACTED]) may be included in the interim analysis.

Figure 3-2 Study Flow Diagram

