6.5.1 Short physical performance battery

[REDACTED]

The Short Physical Performance Battery (SPPB) has been shown to be highly predictive of subsequent disability, hospitalization, institutionalization, and mortality in community-dwelling elders in epidemiological studies and outpatient clinics ([Guralnik et al 2000](#); [Studenski et al 2003](#)). The disability remains even after adjustment for level and severity of comorbidity and self-report functional status. Collectively, SPPB is considered to be a nonspecific but highly sensitive indicator of global health status reflecting several underlying physiological impairments.

The SPPB evaluates lower extremity status by measuring three domains of physical function: maintenance of standing balance, usual gait speed and lower extremity strength and power. The corresponding tasks include three static positions with decreasing base of support to challenge balance, walking at usual speed over 4-meters and, the ability to rise from a chair without the use of the arms once and then five times consecutively. The final score is a composite of the three groups of tasks and uses a standardized scale of 0-12, with the higher score reflecting a higher level of function. A change of 1.0 on the SPPB score is considered clinically relevant ([Perera et al 2006](#), [Pahor et al 2014](#)). Complete details of test administration, equipment and recording into the eCRF are described in the CBYM338E2202 Outcomes Manual.

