9.4.2.1 Analysis for part-A

Part-A is focused on proof of concept of BYM338 on SPPB change from baseline score in older adults with sarcopenia. In this part maximum dose of BYM338 (700mg) will be compared with placebo to establish the following criteria:

[REDACTED]

[REDACTED]

[REDACTED]

[figure not shown]
[REDACTED]

[REDACTED]

[REDACTED]

In addition to the primary objective, additional endpoints of safety (e.g., AEs, lab values, ECG), [REDACTED] background treatments (e.g., exercise, Vitamin D, diet), and efficacy (e.g., gait speed, 6MWT, [REDACTED], [REDACTED], LBM and ASMI by DXA, [REDACTED]) may be included in the interim analysis.

[REDACTED]

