9.6 Sample size calculation

9.6.1 Sample size for primary objective:

Assumptions for part-A:

Decision criteria for part-A is based on the maximum BYM338 dose group (700 mg) and placebo. [REDACTED]

For SPPB, several relevant references are available for judging the standard deviation of SPPB between two time points.

Table 9-1 Standard Deviation of SPPB

Reference	Study description	SD
Perera et al (2006)	N=492 community dwelling adults	1.42
Kwon et al. (2009)	N=424 older sedentary adults	0.46
Papanicolau et al (2013)	N=120 sarcopenic elderly women	1.6

Based on these references, we consider an SD of 1.5 for the change in SPPB from baseline to 6 months to be a realistic estimate while 2.0 is a conservative estimate. [Table 9-2](#) evaluates the power of the comparison between the BYM338 700 mg and placebo groups [REDACTED]

Table 9-2 Power calculation for statistical significance in Part A

Standard Deviation (SPPB points)	Treatment Effect: BYM338 – Placebo (SPPB Points)	Power
1.50	1.1	0.98
	1.2	0.99
	1.3	1.00
	1.4	1.00
	1.5	1.00
1.75	1.1	0.94
	1.2	0.97
	1.3	0.99
	1.4	0.99
	1.5	1.00
2.00	1.1	0.87
	1.2	0.92
	1.3	0.95
	1.4	0.97
	1.5	0.99

Table 9-3 below shows the probability of passing both criteria; that is, achieving significance as well as a point estimate at or exceeding 1 SPPB point.

Table 9-3 Probability of passing dual criteria in Part A

Standard Deviation (SPPB points)	Treatment Effect: BYM338 – Placebo (SPPB Points)	Power
1.50	1.1	0.64
	1.2	0.77
	1.3	0.87
	1.4	0.93
	1.5	0.98
1.75	1.1	0.62
	1.2	0.73
	1.3	0.83
	1.4	0.90
	1.5	0.95
2.00	1.1	0.62
	1.2	0.72
	1.3	0.80
	1.4	0.87
	1.5	0.92

[figure not shown]

Table 9-4 Optimal contrasts used for the power calculation

Dose (mg)	Linear Model (C_1)	E _{max} Model (C_2)	Exponential Model (C_3)
0	-0.4168	-0.7009	-0.3308
70	-0.3155	-0.1622	-0.3043
210	-0.1128	0.1969	-0.2285
700	0.845	0.6661	0.8636

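### The synopsis states the Part A 1-point criterion as a rise from baseline; Section 9.6 and Table 9-3 use a 1-point difference from placebo

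*Protocol*

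**What the plan says.** The Data analysis entry of the synopsis introduces Part A as a test for a "positive effect of maximum bimagrumab dose (700 mg) over placebo in change from baseline SPPB score at week 25". The next sentence defines what counts as positive: "a statistically significant effect over placebo and a clinically relevant improvement of ≥ 1 unit increase from baseline compared to week 25".

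Section 9.6.1 rests the Part A decision criteria on the 700 mg and placebo groups. It describes passing both criteria as "achieving significance as well as a point estimate at or exceeding 1 SPPB point", and Table 9-3 gives that probability by treatment effect, expressed as BYM338 minus placebo. The primary objective (Section 2.1) is the change in SPPB "total score from baseline to week 25 relative to placebo in older adults with sarcopenia".

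Section 6.5.1 gives the relevance threshold with no comparator: "A change of 1.0 on the SPPB score is considered clinically relevant".

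The criteria themselves are announced in Section 3.1.2 ("Following criteria will be evaluated at the end of Part-A") and Section 9.4.2.1 (700 mg "will be compared with placebo to establish the following criteria"), but the text that follows is redacted in both places.

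**The concern.** The synopsis sentence is the only visible definition of a positive Part A effect outside the sample-size section. Its second condition can be met or missed on the 700 mg arm's own change from baseline, whereas Section 9.6.1 needs a 1-point advantage over placebo. Write T and P for the observed mean changes in the 700 mg and placebo arms. Section 9.6.1 then requires T − P ≥ 1, and the literal synopsis wording requires T ≥ 1. These thresholds coincide only when P is exactly 0.

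That cannot be taken for granted. Section 3.2 gives every participant oral nutritional supplements, vitamin D and an exercise programme, so the placebo arm may move from baseline, and the document states no expected placebo change. The rationale for Amendment 3 says Part A results feed strategic decisions about the programme. A reader applying the synopsis could therefore call the result differently from a reader applying Section 9.6.1.

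**Working it through.** **Inputs from the protocol**
- SD of change: 1.5 (realistic), 1.75, 2.0 (conservative); true differences 1.1 to 1.5 (Section 9.6.1, Tables 9-2 and 9-3).
- Planned size: about 100 on 700 mg and 60 on placebo (Section 3.1.1).
- Significance level: "Criterion 1 significant difference updated from one-sided 5% level to one-sided 2.5% level" (Amendment 3, changes to Section 9.4.2.1), hence a critical value of 1.96.

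**Assumptions**
- 85/51 evaluable. No loss rate is visible; this is 85% of 100/60, chosen because it fits Tables 9-2 and 9-3. Results at 100/60 are also given.
- The arm meant by the synopsis clause is 700 mg.
- Expected placebo change is 0, then varied over −0.25 to +0.25.

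**Rules compared** (arm means independent and normal; D = T − P; SE = SD·√(1/n₁ + 1/n₀))
- Between-arm rule (Section 9.6.1): D ≥ max(1, 1.96·SE).
- Literal rule (synopsis): D ≥ 1.96·SE and T ≥ 1.

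**Step 1: reproduce Table 9-3.** At 85/51, √(1/85 + 1/51) = 0.177. SE is therefore 0.266, 0.310 and 0.354 for the three SDs, and the smallest significant difference is 0.52, 0.61 and 0.69. All are below 1, so the 1-point threshold governs and the pass probability is Φ((δ − 1)/SE). For SD 1.5 and δ = 1.1: Φ(0.1/0.266) = 0.65, against 0.64 in the table.

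| SD | Source | 1.1 | 1.2 | 1.3 | 1.4 | 1.5 |
|---|---|---|---|---|---|---|
| 1.5 | Table 9-3 | 0.64 | 0.77 | 0.87 | 0.93 | 0.98 |
| 1.5 | between-arm | 0.647 | 0.774 | 0.871 | 0.934 | 0.970 |
| 1.75 | Table 9-3 | 0.62 | 0.73 | 0.83 | 0.90 | 0.95 |
| 1.75 | between-arm | 0.627 | 0.741 | 0.833 | 0.902 | 0.947 |
| 2.0 | Table 9-3 | 0.62 | 0.72 | 0.80 | 0.87 | 0.92 |
| 2.0 | between-arm | 0.611 | 0.714 | 0.801 | 0.871 | 0.921 |

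The largest gap is 0.011 (0.028 at 100/60).

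**Step 2: try the literal rule on the same table.** With placebo change 0, the largest gap is 0.12 at 85/51 and 0.14 at 100/60. Choosing the single placebo change that fits best still leaves 0.067 (at −0.06, 85/51) or 0.075 (at −0.07, 100/60). Table 9-3 was therefore built on the difference from placebo, whichever evaluable number is used.

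**Step 3: how often the rules disagree.** Probability of opposite decisions, 85/51, placebo change 0:

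| SD | 1.1 | 1.2 | 1.3 | 1.4 | 1.5 |
|---|---|---|---|---|---|
| 1.5 | 0.26 | 0.19 | 0.12 | 0.06 | 0.03 |
| 1.75 | 0.26 | 0.21 | 0.15 | 0.09 | 0.05 |
| 2.0 | 0.24 | 0.20 | 0.15 | 0.11 | 0.07 |

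Here the disagreement comes only from sampling error in the placebo mean (SE 0.21 to 0.28). At SD 1.5 and difference 1.1 it splits into 0.17 passing the literal rule only and 0.09 passing the Section 9.6.1 rule only. The overall pass probabilities in that cell are 0.73 (literal) and 0.65 (between-arm).

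Sensitivity at difference 1.1:
- Placebo change −0.25 / 0 / +0.25: opposite decisions 0.49 / 0.26 / 0.33 (SD 1.5) and 0.41 / 0.24 / 0.25 (SD 2.0).
- At SD 1.5 the literal pass probability over the same range is 0.18 / 0.73 / 0.97, while the between-arm probability stays at 0.65.
- At 100/60 with placebo change 0: 0.26 (SD 1.5) and 0.25 (SD 2.0).

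**Two concrete outcomes** (SD 1.5, 85/51, smallest significant difference 0.52):
- 700 mg +1.1, placebo +0.5: D = 0.6, significant. Passes the synopsis wording (1.1 ≥ 1), fails Section 9.6.1 (0.6 < 1).
- 700 mg +0.8, placebo −0.3: D = 1.1, significant. Fails the synopsis wording (0.8 < 1), passes Section 9.6.1 (1.1 ≥ 1).

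**The case against.** The strongest reply is that context settles the meaning. The preceding synopsis sentence, the primary objective and Section 9.6.1 all point to a comparison with placebo, and Section 6.5.1 describes the instrument rather than a decision rule. The operative criteria sit in redacted text, so a conflict in the rule that will actually be applied cannot be shown. The literal rule used above needs an arm and a placebo change that the document does not supply. Even then the two rules agree in at least 74% of trials in the base case, and in 93% to 97% at a difference of 1.5. Other endpoints may also enter the interim analysis, and no visible text makes the synopsis clause binding.

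Most of this stands as a limit on the point. The intent is very probably the placebo difference, no error is shown in the redacted sections, and the probabilities illustrate the consequence rather than predict it. It does not remove the inconsistency. The sentence that defines a positive effect attaches placebo to one half and baseline to the other. Section 6.5.1 states the same 1-point threshold without a comparator, so the literal reading has some support in the text. If the redacted sections are right, the synopsis disagrees with them; if they repeat its wording, the problem is larger.

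**Conclusion.** The point holds as an inconsistency of wording between the synopsis and Section 9.6.1. It is not an error in the sample size or in Tables 9-2 and 9-3. That Table 9-3 uses the between-arm threshold is firm and does not depend on the assumed evaluable numbers. That the synopsis clause is only loosely worded is likely but cannot be confirmed from the visible text.

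If the clause were followed as written, the decision would differ from that of Section 9.6.1 in roughly a quarter of trials at a true difference of 1.1, falling to 3% to 7% at 1.5. This assumes 85/51 evaluable, the 700 mg arm and an expected placebo change of 0. At a difference of 1.1, a placebo change of −0.25 raises the figure to 0.41 to 0.49, and one of +0.25 gives 0.25 to 0.33. It should be corrected before the Part A data are unblinded.

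**What to change.** Reword the synopsis clause to: *a statistically significant difference from placebo and an estimated difference (bimagrumab 700 mg minus placebo) in SPPB change from baseline to week 25 of at least 1 point*. Confirm that the criteria in Sections 3.1.2 and 9.4.2.1 say the same. Do both before the Part A unblinding.

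The cost is one clause and a check of two sections. No patients, extra data, sample-size change or table revision is needed.
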